## 2.1.2 Exclusion Criteria

2.1.2.1 Participants with platelet transfusion-refractory thrombocytopenia, with inability to keep platelet threshold above 10K/mcL with transfusions or those with ongoing or uncontrolled hemorrhagic complications.

2.1.2.2 Participants with clinically significant neutropenia, defined as ANC <100 cells/mcL with frequent hospitalizations for infection (average > 1 hospitalization per month in the past 6 months).

2.1.2.3 Participants on treatment with a myeloid growth factor (e.g., G-CSF) within 14 days prior to initiation of study treatment.

2.1.2.4 History of allergic reactions attributed to compounds of similar chemical or biologic composition to HMAs or other agents used in study.

2.1.2.5 Uncontrolled intercurrent illness evaluated by history, physical exam, and chemistries or situations that would limit compliance with study requirements, interpretation of results or that could increase risk to the participant

2.1.2.6 Participants with the following cardiac conditions: symptomatic congestive heart failure, unstable angina pectoris, or uncontrolled cardiac arrhythmia as assessed by electrocardiogram (ECG).

- 2.1.2.7 Pregnancy (confirmed with  $\beta$ -HCG serum or urine pregnancy test performed in individuals of childbearing potential at screening)
- 2.1.2.8 Presence of any other malignancy (except basal and squamous cell carcinoma of the skin, or stable chronic cancers on hormone or targeted therapy) for which participant received systemic anticancer treatment (except maintenance therapy) within 24 months prior to treatment.
- 2.1.2.9 Participants with active/uncontrolled Hepatitis B
- 2.1.2.10 Participants with active/uncontrolled Hepatitis C
- 2.1.2.11 Participants with active/uncontrolled HIV infection or AIDS.
- 2.1.2.12 Participants currently taking contraindicated medications for HIV, Hepatitis B, or Hepatitis C disease control ([Appendix L](#))

### 2.1.3 Recruitment Strategies

This protocol will be advertised on NIH websites (clinicaltrials.gov, future Myeloid Malignancy Program Web Site) and social media platforms, as well as through professional MDS associations.

## 2.2 SCREENING EVALUATION

### 2.2.1 Screening activities performed prior to obtaining informed consent

Minimal risk activities that may be performed before the subject has signed a consent include the following:

- Email, written, in person or telephone communications with prospective subjects
- Review of existing medical records to include H&P, laboratory studies, etc.
- Review of existing MRI, x-ray, or CT images
- Review of existing photographs or videos
- Review of existing pathology reports from a specimen obtained for diagnostic purposes

### 2.2.2 Screening activities performed after a consent for screening has been signed

The following activities will be performed only after the participant has signed the consent for this study for screening. Assessments performed at outside facilities or on another NIH protocol within the timeframes listed below may be used to determine eligibility once a participant has signed the consent for this study.

Assessments and procedures to confirm study eligibility should be completed within 30 days prior to the start of treatment, unless otherwise indicated. See also Section [3.5](#), Study Calendar.

#### Any time prior (no time limit):

- Histologic confirmation: All participants are required to have histologically confirmed MDS. If pathology reports are from outside institutions, outside slides pathologic review of diagnosis by Laboratory of Pathology of NCI is required to determine study eligibility at screening.

#### Within 30 days:

- History and physical examination: Complete history and physical examination (including height, weight, vital signs, and performance status)
- Laboratory Evaluation:
  - Hematological Profile: CBC with differential, reticulocyte count
  - Biochemical Profile: total bilirubin, BUN, albumin, calcium, creatinine, SGOT [AST], SGPT [ALT], phosphorous, magnesium, potassium, sodium, LDH, uric acid, ferritin, endogenous erythropoietin
  - Vitamin B12, folate, copper, zinc, TSH, free T4- to assess alternative/reversible causes of cytopenias that may confound MDS diagnosis
  - Infectious serologies including HIV, HBV, HCV
  - Urine and/or serum pregnancy test for individuals of childbearing potential (must be performed within 24 hours prior to initiating study treatment)
- Cardiac Evaluation: Electrocardiogram (ECG)
- Next Generation Sequencing (as needed): panel of myeloid genes from bone marrow. May be performed during screening evaluation if the MDS diagnosis is in question based on histology alone.
- Bone marrow aspirate and biopsy (as needed): if no prior sample is available for pathology review, a fresh bone marrow aspirate and will be taken at screening to determine diagnosis.

## 2.3 PARTICIPANT REGISTRATION AND STATUS UPDATE PROCEDURES

Registration and status updates (e.g., when a participant is taken off protocol therapy and when a participant is taken off-study) will take place per CCR SOP ADCR-2, CCR Participant Registration & Status Updates found <https://ccrod.cancer.gov/confluence/pages/viewpage.action?pageId=73203825>.

### 2.3.1 Screen Failures

Screen failures are defined as participants who consent to participate in the clinical trial but are not subsequently assigned to the study intervention or entered in the study. A minimal set of screen failure information is required to ensure transparent reporting of screen failure participants, to meet the Consolidated Standards of Reporting Trials (CONSORT) publishing requirements and to respond to queries from regulatory authorities. Minimal information includes demography, screen failure details, eligibility criteria, and any serious adverse event (SAE).

Individuals who do not meet the criteria for participation in this trial (screen failure) because of any specific inclusion/exclusion criteria by discretion of PI may be rescreened.

Circumstances when a participant may be re-screened:

1. If a participant consented to participate and met the eligibility criteria, but there was a delay in starting due to a change in situation (e.g., family issues, individual request for attending a private matter, etc.)
2. If a participant previously failed screening due to an acute event that has now resolved/reversed.

3. If a participant failed screening due to being on a prohibited medication, which has been discontinued.
4. If reversible causes of screen failure have been adequately treated.

### 2.3.2 Treatment Assignment (for Phase I and II)

#### Cohorts

Number	Name	Description
1	Phase I- “Higher-risk” MDS	Participants with confirmed MDS and IPSS-R score > 3.5 (high and higher intermediate-risk)
2	Phase II- “Higher-risk” MDS	Participants with confirmed MDS and IPSS-R score > 3.5 (high and higher intermediate-risk) for phase II dose expansion

#### Arms

Number	Name	Description
1	Phase I- Dose escalation of KPT-8602 for HR-MDS	Inqovi for 5 days, followed by escalating doses of KPT-8602
2	Phase II- Dose expansion for HR-MDS	Inqovi for 5 days, followed by Phase II dose of KPT-8602

#### Arm Assignment

Participants in Cohort 1 will be directly assigned to Arm 1; Cohort 2 will be directly assigned to Arm 2;

## 3 STUDY IMPLEMENTATION

### 3.1 STUDY DESIGN

The study consists of two phases:

- Phase I: Safety evaluation with determination of the recommended phase 2 dose (RP2D) of KPT-8602 in combination with Inqovi, and
- Phase II: Efficacy evaluation of KPT-8602 in combination with Inqovi

Participants will be enrolled into one of two cohorts, depending on the phase of study as follows:

- Phase I:
  - **Cohort 1:** Participants with higher-risk MDS that will be treated with Inqovi for 5 days, followed by KPT-8602 at escalating doses.
- Phase II:
  - **Cohort 2:** Participants with higher-risk MDS that will be treated with Inqovi for 5 days, followed by KPT-8602 at the RP2D.

In Phase I, participants enrolled in Cohort 1 will be treated with Inqovi 35 mg/100 mg daily on Days 1-5 of each 28-day cycle, plus KPT-8602 at the corresponding dose level and schedule..

Dose-escalation will follow a standard 3+3 design (see Section [3.1.2](#)), with DLT assessment during the first 28 days of treatment.

In Phase II, participants enrolled in Cohort 2 will be treated with Inqovi 35 mg/100 mg daily on Days 1-5 of each 28-day cycle, plus KPT-8602 at the RP2D identified in Phase I.

The study drugs will be self-administered by the patient, except on days of PK blood draws.

Participants in Cohorts 1 and 2 are eligible to participate in the study if they have received a minimum of 4 cycles of HMA therapy with inadequate response (failure to achieve at least a PR, or experienced disease progression prior to completing 4 cycles). For participants on HMA therapy with Inqovi prior to enrollment, descriptions of initiation of study therapy refer to initiation of KPT-8602 only. Of note, participants receiving Inqovi prior to enrollment must be on the standard dose (35 mg decitabine and 100 mg cedazuridine) without prior dose-reductions.

In both Phase I and Phase II, participants will continue treatment until disease progression, death, unacceptable toxicities as listed in Section [3.3.2](#), or another off-treatment criterion is met (see Section [3.7.1](#)) as long as no other contraindications to further treatment. Participants that do not achieve at least partial remission following cycle 6 will not receive additional treatment.

Blood samples for correlative research will be collected (Section [5.1](#)). Participants may be admitted on day 8 of cycle 1 for pharmacokinetics (PK) studies to be performed, and on other days if necessary or for convenience.

Upon discontinuation of study treatment, participants will be followed for safety for at least 30 days after the last dose of treatment, and for event-free survival (EFS), progression-free survival (PFS), and overall survival (OS) until study follow-up requirements have been completed. The study will be closed to follow-up when all enrolled participants have been followed for up to 8 years or have died.

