#### 1.2.3.2 Dosing

As of 18 November 2023, a total of 153 patients (39 patients with R/R MM, 30 patients with RR CRC, 30 patients with mCRPC, and 50 patients with HR-MDS, and 4 with ND MDS) have received eltanexor on Study 801 and have safety data available. In addition, 3 patients have been dosed in Part F Phase 2 (HR-MDS) and 2 patients in Part G (newly diagnosed intermediate or high risk MDS in combination with Inqovi); however, no safety data is available as of the cut-off date in these 5 patients.

In the dose escalation phase, which is now complete, patients with R/R MM were dosed with 5-40 mg eltanexor daily x 5 days (5 days on, 2 days off) per week or 60 mg eltanexor every other day x 3 doses (every other day for 5 days, 2 days off), alone or in combination with dexamethasone. There were 2 DLTs observed (>4 missed doses and Grade 4 thrombocytopenia) in different dose cohorts, however, the protocol-defined MTD was not reached.[\(37\)](#) Therefore, both 20 mg and 30 mg eltanexor daily x 5 + 20 mg dexamethasone twice weekly were selected for further evaluation to clearly define the recommended phase 2 dose (RP2D).

In the dose-expansion phase, patients with mCRC were dosed at 20 or 30 mg eltanexor daily x 5, mCRPC patients were dosed at 20 or 30 mg eltanexor daily x 5 alone or in combination with abiraterone, and HR-MDS patients were dosed at 10 or 20 mg eltanexor x 5 (5 days on, 2 days off, in 28-day cycles).

In patients with HMA-refractory HR-MDS (n = 35) treated with single-agent eltanexor, the median duration of eltanexor (10 mg) was 19.1 weeks (range 2 to 85); however 10 patients treated for  $\geq$  24 weeks. In 10 mg cohort (n = 5), 3 patients (60%) had marrow complete response (mCR) and 2 patients (40%) had stable disease (SD). In the 20 mg cohort (n = 10), 4 patients (40%) had mCR and 3 (30%) had SD. The overall survival (OS) for all patients was 9.9 months, and 11.9 months for those achieving mCR vs 8.7 months for those who did not achieve mCR (hazard ratio = 0.27, p=0.05). [\(38\)](#)

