**Hematologic criteria to start the next cycle (applies only to participants without active disease by bone marrow):**

- ANC  $\geq$  1000/mcL
- PLT  $\geq$  50,000/mcL

Participants who do not meet these hematologic criteria (and without active disease by bone marrow) should have the next cycle delayed and CBC monitored at least weekly until ANC is  $\geq$  1000/mcL and PLT  $\geq$  50,000/mcL.

- If hematologic recovery (ANC  $\geq$  1000/mcL and PLT  $\geq$  50,000/mcL) occurs within 2 weeks of achieving remission by bone marrow, continue Inqovi and KPT-8602 at the same dose for the next cycle.
- If hematologic recovery does not occur within 2 weeks of achieving remission by bone marrow, delay Inqovi and KPT-8602 for up to 2 additional weeks and dose-reduce for the next cycle as noted below:

Dose reduction	Inqovi dosage*	KPT-8602 dosage*
First	Continue same dose	Reduce by one dose level
Second	Reduce by one dose level	Reduce by one dose level
Third	Reduce by one dose level	Reduce by one dose level
Fourth	Reduce by one dose level	Permanently discontinue

*\*Once the lowest dose level has been reached for a given drug, if myelosuppression persists, discontinue drug.*

If not resolved within 8 weeks participant will be taken off treatment.

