### **3.7.1 Criteria for removal from protocol therapy**

- Progressive disease
- Participant requests to be withdrawn from active therapy
- Toxicities (see Section [3.3.2](#))
- Lack of, at least partial remission, after 6 cycles of therapy
- Investigator discretion
- Positive pregnancy test

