#### 6.3.1 Response Criteria

The table below shows the 2006 International Working Group response criteria for altering the natural history of MDS,[\(55\)](#) with modified definitions for HI-E, HI-P, and HI-N in the suggested 2018 International Working Group response criteria.[\(54\)](#)

Category	Response criteria (responses must last at least 4 weeks)
Complete remission	

• Bone marrow: <math>\leq 5\%</math> myeloblasts with normal maturation of all cell lines*

• Persistent dysplasia will be noted*

• Peripheral blood†

• Hgb <math>\geq 11</math> g/dL

• Platelets <math>\geq 100 \times 10^9/L</math>

• Neutrophils <math>\geq 1.0 \times 10^9/L</math>

• Blasts 0%

Category	Response criteria (responses must last at least 4 weeks)
Partial remission	All CR criteria if abnormal before treatment except: 
 
• Bone marrow blasts decreased by <math>\geq 50\%</math> over pretreatment but still <math>> 5\%</math>
 
• Cellularity and morphology not relevant
 

Marrow CR	
 
• Bone marrow: <math>\leq 5\%</math> myeloblasts and decrease by <math>\geq 50\%</math> over pretreatment
 
• Peripheral blood: if HI responses, they will be noted in addition to marrow CR
 

Stable disease	Failure to achieve at least PR, but no evidence of progression for $> 8$ wks
Failure	Death during treatment or disease progression characterized by worsening of cytopenias, increase in percentage of bone marrow blasts, or progression to more advanced MDS FAB subtype than pre-treatment
Relapse after CR or PR	At least 1 of the following: 
 
• Return to pre-treatment bone marrow blast percentage
 
• Decrement of <math>\geq 50\%</math> from maximum remission/response levels in granulocytes or platelets
 
• Reduction in Hgb concentration by <math>\geq 1.5</math> g/dL or transfusion dependence
 

Cytogenetic response	
Complete
 
 
• Disappearance of the chromosomal abnormality without appearance of new ones
 
 
Partial
 
 
• At least 50% reduction of the chromosomal abnormality
 

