## 10 STATISTICAL CONSIDERATIONS

### 10.1 OBJECTIVES AND ENDPOINTS

OBJECTIVES	ENDPOINTS	JUSTIFICATION FOR ENDPOINTS
Primary		
Phase I: To determine the recommended phase 2 dose (RP2D) of KPT-8602 in combination with Inqovi in adult participants with higher-MDS	- Recommended phase 2 dose (RP2D), as determined by the number of participants with DLTs reported at each dose level studied (Section 3.1.1 ) -Any toxicities identified from Day 1 of study drug through 28 days after the first dose. AEs are reported by type and grade. -ORR (defined as CR+PR+mCR with HI) per each cohort Responses will be assessed after every cycle with CBC and at the end of Cycles 2 and 6 with bone marrow assessment during treatment and every 3-6 months after that until time of disease relapse, disease progression, or death, or 8 years, whichever occurs first.	Standard endpoint for Phase I protocol Efficacy evaluation, standard for Phase II protocol
Secondary		
Phase I: To characterize the PK properties of KPT-8602 in combination with Inqovi in MDS participants	-AUC, half-life, and steady state concentration, measured by the KPT-8602 blood concentration 1, 2, 3, 4, 8, 24 and 48 hours after the product administration on days 8 and 21 of cycle one	PK studies to evaluate for adequate absorption of therapy and further define half-life/AUC and other properties of the study drug, when given in combination with Inqovi
Phase II: To further evaluate the PK properties and safety of KPT-8602 in combination with Inqovi in MDS participants	-Safety, as measured by: Incidence of AEs, SAEs; and AEs leading to discontinuation, death, and laboratory abnormalities, assessed at least weekly through cycle 3 and then at the start and every cycle after that	Confirm safety of the study drug at the RP2D
Exploratory		
To evaluate the relationship between KPT-8602 exposure (PK) and response	Each of these will be evaluated using descriptive methods and reported as exploratory results. If any statistical	Evaluate mechanism of the study drug, target engagement,

OBJECTIVES	ENDPOINTS	JUSTIFICATION FOR ENDPOINTS

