#### Data collection during study/treatment

- Cycle number & day of treatment
- Study Drug Administration
- Disease response at assessment timepoints: CR (complete response), PR (partial response), HI (hematologic improvement), mCR with HI (marrow CR with hematologic improvement), mCR without HI (marrow CR without hematologic improvement), SD (stable disease), PD (disease progression)
- Best overall response to study treatment: CR (complete response), PR (partial response), HI (hematologic improvement), mCR with HI (marrow CR with hematologic improvement), mCR without HI (marrow CR without hematologic improvement), SD (stable disease), PD (disease progression)
- Bone marrow percent blasts
- RBC transfusion dependence (transfusion dependent or transfusion independent)
- Platelet transfusion dependence (transfusion dependent or transfusion independent)
- # of transfusions per month (RBCs units and instances of platelets transfusions)
- Adverse events
- Patient Reported Outcome Questionnaires: (per section 3.5.3)

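### Marrow CR with hematologic improvement counts toward the primary ORR, but the cycle 6 rule as worded takes these responders off treatment

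*Combined protocol and SAP*

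**What the plan says.** Section 10.1 defines the primary efficacy endpoint as "ORR (defined as CR+PR+mCR with HI) per each cohort".

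Section 3.1 sets the limit on treatment: "Participants that do not achieve at least partial remission following cycle 6 will not receive additional treatment". Section 3.7.1 repeats it in the list of reasons for removal from protocol therapy: "Lack of, at least partial remission, after 6 cycles of therapy". Neither place mentions marrow CR.

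The response table in section 6.3.1 gives marrow CR its own row. That row sets a marrow blast criterion and no blood-count threshold, and adds "Peripheral blood: if HI responses, they will be noted in addition to marrow CR". Appendix I has the database record PR, "mCR with HI (marrow CR with hematologic improvement), mCR without HI (marrow CR without hematologic improvement") and stable disease as separate outcomes.

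**The concern.** The endpoint and the continuation rule use different lists of responses. The endpoint accepts three categories. The rule, taken at its word, accepts two. The category left out is a success for the trial and, at the same visit, a reason to withdraw treatment for lack of response.

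The first thing at stake is patient care: a participant who is responding by the trial's own definition would lose continued therapy and any chance of a later CR. The second is how late responses are documented. A response first seen when treatment stops has to prove its duration without the drug. The third is consistency: if investigators read the phrase differently, identical participants will be handled differently.

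**Working it through.** **1. The plan's own design figures.** This point disputes none of them. Inputs from section 10.2: p0 = 0.25, p1 = 0.45, first stage 21 (stop at 5 or fewer), total 43 (success at 17 or more).

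- Probability of early termination under p0: sum over x = 0 to 5 of C(21,x) × 0.25^x × 0.75^(21−x) = 0.5666. The plan states 56.7%.
- Probability of success: sum over x = 6 to 21 of P(X1 = x) × P(X2 ≥ 17 − x), where X1 is the response count among the first 21 and X2 among the remaining 22. At p0 this is 0.0245; at p1 it is 0.8005. Both agree with two-sided alpha 0.05 (0.025 in one tail) and beta 0.20.

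The boundaries depend only on the response list in section 10.1, so a change to the treatment rule leaves them alone.

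**2. The two lists side by side.** Definitions are from section 6.3.1, the ORR column from section 10.1, and the last column from sections 3.1 and 3.7.1 read literally.

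| Category | Marrow blasts | Blood counts | In ORR | Treated after cycle 6 |
|---|---|---|---|---|
| CR | 5% or less | CR thresholds | yes | yes |
| PR | halved or better, still above 5% | CR thresholds, where abnormal before treatment | yes | yes |
| Marrow CR with HI | 5% or less and halved or better | no CR threshold; HI present | yes | **no** |
| Marrow CR without HI | 5% or less and halved or better | none | no | no |

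Counted responders: {CR, PR, marrow CR with HI}. Allowed to continue: {CR, PR}. The difference is {marrow CR with HI}.

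PR and marrow CR cannot overlap, because blasts cannot be both above 5% and at most 5%. A participant with blasts of 5% or less meets the literal threshold only by being a full CR. The definitions do not rank the two categories either: marrow CR is the deeper marrow result, PR the fuller count recovery.

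**3. Timing.** The study calendar for cycle 2 onward (section 3.5.2) requires phase II marrows at C2D28 and C6D28, each ± 3 days.

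- Gap between them: (6 − 2) × 28 = 112 days = 16 weeks. Without an extra, clinically indicated marrow, a marrow CR that begins in this gap is first documented at C6D28, just as the rule takes effect.
- Section 6.3.1 requires responses to last at least 4 weeks. Counted from C6D28, that falls in what would have been cycle 7, with no protocol drug.
- Erythroid HI needs at least 8 weeks. If it has already lasted w weeks at C6D28, the part left to show off drug is max(0, 8 − w), so from 0 to 8 weeks. C6D28 is week 24 (6 × 28 = 168 days), so an erythroid improvement that began by week 16 and has held is already complete.

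**4. Number affected.** If the trial ended exactly on its success boundary of 17/43 (39.5%), the responders in marrow CR with HI could number anything from 0 to 17. No figure in the documents narrows that range.

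**The case against.** **The phrase may already include marrow CR.** Section 6.3.1 defines stable disease as "Failure to achieve at least PR, but no evidence of progression for" more than 8 weeks. If marrow CR fell short of that threshold, every lasting marrow CR without progression would also be stable disease, yet Appendix I keeps the two apart. This is a fair inference and would remove the conflict. But no text states it, and the removal criterion should not depend on inference from another row.

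**A strict rule may be deliberate.** The inclusion criterion in section 2.1.1 uses the same PR threshold to define inadequate response to prior hypomethylating therapy, and a continuation threshold need not equal an activity endpoint. This stands as a possibility. If it is the intent, the protocol does not say so.

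**The ORR is not changed.** This is correct for responses already confirmed by cycle 6, and section 3.1 continues follow-up for EFS, PFS and OS after treatment. It does not cover a response first documented at C6D28.

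A reader might also infer three stronger points that the documents do not support.

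- *That section 3.3.2.1 contradicts the rule.* It says that if hematologic recovery "occurs within 2 weeks of achieving remission by bone marrow, continue Inqovi and KPT-8602 at the same dose for the next cycle". This is a count-recovery condition for people still on therapy, and section 3.1 makes treatment subject to the off-treatment criteria of section 3.7.1. A participant with a cleared marrow and partly recovered platelets need not have HI, so need not be a responder at all.
- *That most responders would be stopped.* Section 1.2.3.2 reports "In 10 mg cohort (n = 5), 3 patients (60%) had marrow complete response (mCR) and 2 patients (40%) had stable disease (SD"). Those patients had eltanexor alone, 20 days in 28 (section 3.1.2), and their HI status is not given. The figures give no rate of marrow CR with HI for this combination.
- *That the trial loses power.* This would require the share of responders first documented at C6D28 who then lose the response off drug before it is confirmed. The documents give no such figure.

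**Conclusion.** The point holds as a mismatch of wording with a clinical consequence. Applied as written, sections 3.1 and 3.7.1 take a primary-endpoint responder in marrow CR with HI off treatment for lack of response. Such a response first documented at C6D28 must complete its 4 weeks, and any outstanding part of the 8 weeks for erythroid HI, without protocol drug.

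The size is unknown and may be zero. The conclusion rests on the literal meaning of PR as section 6.3.1 defines it, and on the absence of any exemption. The looser reading is plausible but unwritten. The validity of the Simon design is not in question. The amendment is still worth making, because the correction is small and the text leaves investigators to guess.

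**What to change.** In sections 3.1 and 3.7.1, replace *at least partial remission* with *a response (CR, PR or marrow CR with HI)*, so that the cycle 6 rule uses the list in section 10.1. Add that a response first seen at the cycle 6 assessment allows treatment to continue while its required duration is confirmed; without this, the new wording would leave open whether an unconfirmed response permits cycle 7.

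If the sponsor does mean to stop participants in marrow CR with HI, both sections should say so explicitly.

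The cost is an amendment to two sections, plus longer drug exposure and more drug supply for the participants concerned. N = 43 and the boundaries 6/21 and 17/43 are unchanged.
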